7.2.5 Blood samples (facultative)

At randomization and the end of the protocol (48 hours) in both groups (supine and prone), and for those centers that have the storage capacity, blood samples (2 x 5 ml in EDTA, citrate, and heparin) will be collected and stored at -80°C for measurement of markers of lung injury (angiopoietin-2, surfactant proteins D, RAGE). Blood samples will be sent and processed at a central laboratory.

7.2.6 Assessment of regional ventilation (facultative)

Before (in supine) and at the end of the first and the last prone position, for those centers with electrical impedance tomography, we plan to investigate the effects of global and regional end-expiratory lung impedance variation (Δ EELI).

8. STATISTICAL ANALYSIS

8.1 Descriptive statistics

Patient characteristics will be compared and described by appropriate statistics.

8.2 Analysis

The goal of the primary outcome is to quantify the effect of prone position versus the standard treatment upon the need for invasive mechanical ventilation during the first fourteen days after randomization.

Interim analyses for efficacy and futility will be conducted at 50% (N= 357), 75% (N= 476), and 100% (N= 714) of the planned enrollment, as needed, using a non-binding group sequential design with gamma spending functions (gamma = -4 for each of alpha and beta).

The table below shows the alpha and beta spent over the trial, z-statistic boundaries for efficacy and futility, and boundary-crossing probabilities under the alternative hypothesis (H1). The corresponding P-value boundaries for efficacy (futility in parentheses) at the 1st, 2nd and final looks, respectively, are P≤ 0.006 (P>0.82), P≤ 0.015 (P>0.35), and P ≤ 0.044 (P>0.044). The Figure below displays the z-statistic boundaries for efficacy/harm and futility as a function of accrued sample size.

For the primary efficacy analysis rates of invasive mechanical ventilation will be compared between the two intervention groups, and the odds ratio relative risks with corresponding 95% confidence levels interval will be calculated using logistic regression analysis.

With regard to the remaining parameters: Normally distributed variables will be expressed by their mean and standard deviation; non-normally distributed variables will be expressed by their medians and interquartile ranges. Categorical variables will be expressed as n (%).

Student's t-test will be used to test groups of continuous normally distributed variables.

Conversely, if continuous data is non-normally distributed, the Mann-Whitney-U test will be used. Categorical variables will be compared with the Chi-square test, Fisher's exact tests, or, where appropriate, as relative risks. Time-dependent data will be analyzed using a proportional hazard model adjusted for possible imbalances of patients' baseline characteristics.

COVID-19 status of patients will be taken into account and analyzed in the study to find any

differences in the primary and secondary outcomes between COVID-19 and non-COVID-19 patients.

A stratified analysis will be done by the device used (HFNC, BIPAP, CPAP, and their interfaces).

The statistical analysis will be based on the intention-to-treat principle. Besides, we will perform a per-protocol analysis to check for the robustness of the results. The intention-to-treat analysis includes all patients as randomized regardless of whether they received the randomized treatment or other protocol deviations. Per-protocol group analysis only considers those patients who completed the treatment according to the originally allocated protocol.

Data analyses will follow an a priori documented statistical analysis plan, which will be finalized before the end of data collection. By definition, only the analysis of the primary outcome is confirmatory; all other analyses are exploratory. The analysis strategy follows the intention-to-treat principle. The analysis will be undertaken blinded by a statistical expert. Statistical significance is considered to be at a p-value of 0.05, where 95% confidence levels will express appropriate statistical uncertainty.

The analysis will be performed with R statistics.

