6.4 Sample size calculation

The initial sample size calculation was based on our primary hypothesis and primary study outcome. The required sample size was calculated using data from a multicenter randomized controlled trial reporting intubation rate in patients with acute hypoxemic respiratory failure with a PaO₂/FiO₂ ratio less than 200 using HFNC²⁵.

These calculations indicated that 322 patients would be required per group, assuming a twosided significance level of 0.05 and a power of 80%, to detect the expected difference in the

rate of mechanical ventilation between the prone position group of 24 % and the standard treatment group of 34 % (risk ratio of 0.70). Assuming a dropout rate of 10%, **a total of 714 patients** (n= 357 per group) were planned to be included in the study.

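### The second interim look is given as both 75% and N=476, which is 66.7% of 714; the printed stopping limits fit only a 75% look, and the protocol does not say which of the two triggers it

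*Protocol*

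**What the plan says.** Section 8.2 of the protocol plans analyses for efficacy and futility at "50% (N= 357), 75% (N= 476), and 100% (N= 714) of the planned enrollment", "using a non-binding group sequential design with gamma spending functions (gamma = -4 for each of alpha and beta"). The P-value limits for efficacy, with futility in brackets, "are P≤ 0.006 (P>0.82), P≤ 0.015 (P>0.35), and P ≤ 0.044 (P>0.044"). The section also refers to a boundary table and to a figure that "displays the z-statistic boundaries for efficacy/harm and futility as a function of accrued sample size"; neither can be seen in the text available for review.

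Section 6.4 supplies the other design inputs: two-sided 0.05, 80% power, 24% versus 34% needing invasive ventilation, 322 per group, and 10% dropout, giving 714. The total of 714 is repeated in sections 6.1 and 7.2.

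**The concern.** A spending-function limit is valid only for the information fraction at which it was calculated. Here one look carries two different fractions, 75% by label and 66.7% by count, and the two are 60 patients apart, which is too far for rounding. A coordinating center may well schedule the look by counting patients. If it does so at 476 and the data safety board then applies the printed limits, two bands of results would be read differently from what the stated spending functions imply:

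- a P-value between 0.0097 and 0.015 would signal efficacy;
- a P-value between 0.35 and 0.57 would signal futility.

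In both bands the stated functions say continue.

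**Working it through.** **Inputs.** From section 8.2: gamma = -4 for alpha and for beta, non-binding futility, boundaries for efficacy/harm and futility. From section 6.4: two-sided alpha 0.05, power 80% (beta 0.20), 34% versus 24%, 10% dropout, maximum 714. Assumption: futility is a two-sided inner region, |Z| below a limit. This matches the way the futility P-values are printed and, as step 3 shows, reproduces them.

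**1. Fractions.** 357/714 = 0.500; 476/714 = 0.667; 714/714 = 1. And 0.75 × 714 = 535.5, so about 536; 536 − 476 = 60.

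**2. Spending allowed.** The gamma function with parameter -4 spends the share (e^(4t) − 1)/(e^4 − 1) by fraction t.

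| t | share | two-sided alpha (× 0.05) | beta (× 0.20) |
|---|---|---|---|
| 0.500 | 0.1192 | 0.0060 | 0.024 |
| 0.667 | 0.2499 | 0.0125 | 0.050 |
| 0.750 | 0.3561 | 0.0178 | 0.071 |

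**3. Limits.** These come from recursive numerical integration. Efficacy limits ignore futility, because futility is non-binding. The drift (expected Z at full information) is solved so that total type II error is 0.20.

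| | Printed | Looks at 50/75/100% | Looks at 50/66.7/100% |
|---|---|---|---|
| Look 1 efficacy | 0.006 | 0.0060 (z 2.750) | 0.0060 (z 2.750) |
| Look 1 futility | 0.82 | 0.822 | 0.824 |
| Look 2 efficacy | 0.015 | 0.0150 (z 2.432) | 0.0097 (z 2.586) |
| Look 2 futility | 0.35 | 0.353 | 0.573 |
| Final efficacy | 0.044 | 0.0442 (z 2.012) | 0.0455 (z 2.000) |

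The 50/75/100% column reproduces every printed value. The 50/66.7/100% column misses the three that depend on the second look.

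**4. Type I error if the printed limits are used at N=476, futility ignored.** Cumulative two-sided alpha is 0.0060, 0.0172 and 0.0508 (0.0510 with unrounded limits). At look 2 that is 0.0172 against 0.0125 allowed. The printed final limit, 0.044, is slightly stricter than the 0.0455 that a 66.7% look would give. This partly offsets the excess, and the total stays near 0.051.

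**5. Behaviour under the planned effect.** With 10% dropout, 714 × 0.9 / 2 = 321 per group. The drift for 34% versus 24% is 0.10/√(2 × 0.29 × 0.71/321) = 2.79 with pooled variance and 2.81 unpooled; 2.80 is used. All rows use this same drift, with futility followed.

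| Limits and timing | Futility by look 2 | Power |
|---|---|---|
| Printed limits, look 2 at 66.7% | 9.4% | 77.6% |
| Printed limits, look 2 at 75% | 7.9% | 78.3% |
| Matching limits, look 2 at 66.7% | 5.4% | 78.6% |

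Before rounding, the first two powers are 77.62% and 78.27%. The mismatch therefore costs about 0.65 of a point against the 75% design and 1.0 point against the matching two-thirds design.

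**The case against.** The strongest reply is that this is one wrong count in a coherent design. The 75% label, the spending functions and all the printed P-values agree with one another; only 476 does not. If the look is taken at 75%, every limit is right and nothing in the error control changes. That stands, and it makes the harm conditional on the look being taken at 476. It does not remove the contradiction, because nothing in section 8.2 ranks the percentage above the count.

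The futility limit is also non-binding, and the looks are to be made only as required, so crossing P>0.35 is advice and does not compel a stop. That stands too. The efficacy limit at look 2 is not softened in this way.

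Dropout might be thought to explain 476. Against 2 × 322 = 644 evaluable patients, 476 is 73.9%. But 357 would then be 55.4%, not 50%, and section 8.2 defines the fractions on planned enrollment. This explanation fails.

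A separate statistical analysis plan may give more detail, but the protocol itself fixes both the count and the limits, so the conflict lies in what it states.

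**Conclusion.** The protocol contradicts itself on when the second look happens, and its limits fit only the 75% reading. This is certain from arithmetic and from exact reproduction of the printed limits. If the look is taken at N=476 with those limits, the efficacy limit is too lenient (0.015 against 0.0097) and the futility limit too aggressive (P>0.35 against P>0.57). The consequences are concentrated at that look; overall, alpha is about 0.051 and power falls by about 0.6 to 1.0 percentage point.

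Three stronger readings are tempting and are not supported:

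- *The printed boundaries are wrong as such.* They are correct for a true 75% look, and the protocol does not say that 476 governs.
- *The error lowers power from the planned 80% to 77.6%.* Most of that gap is the ordinary cost of interim looks on a sample size that matches a fixed design. It remains at 78.3% or 78.6% once count and limits agree.
- *Futility stops rise from the 5.0% allowed to 9.4%.* The 5.0% budget is defined at the drift that gives 80% power in the sequential design (about 2.85), and the 9.4% is calculated at 2.80. The like-for-like figure is 5.4%.

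The results assume inner-region futility with beta 0.20 and, for the futility and power figures, the planned rates and dropout. The efficacy limits and the alpha figures do not depend on the rates or the dropout.

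**What to change.** Choose one consistent design before the second look:

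- **Keep 75%:** change the second look to N=536 and leave every printed limit as it is; or
- **Keep N=476:** relabel it 67% and print look 2 efficacy P≤0.0097, look 2 futility P>0.57 and final efficacy P≤0.0455. The look 1 limits do not change.

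Then check that the boundary table and figure, which could not be seen here and may already be right, agree with the choice. The cost is one sentence of section 8.2, plus the table and figure if they need it. The maximum sample size stays at 714.

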7. METHODS

7.1 Study parameter/endpoints

7.1.1 Main study parameters/endpoint

• Rate of invasive mechanical ventilation during the first fourteen days of enrolment

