7.2.4 Data to be collected

The documentation of the data will adhere to the timetable in APPENDIX v.

Pre-randomization variables

Pre-randomization variables will be collected:

- Gender and age; female + years
- Height and weight; kg + cm
- Date and time of hospital admission
- Source of admission to the ICU (emergency department, hospital ward, transfer from another ICU, transfer from a non-ICU ward of another hospital)
- Date and time of ICU admission
- Type of non-invasive respiratory support (HFNC, NIV, CPAP)
- COPD with inhalation therapy and/or steroids
- Smoking status; never, former (at least three months prior) or current
- History of active cancer; if yes, specify the type of cancer
- History of diabetes mellitus; oral medication or insulin therapy
- History of hypertension
- Use of angiotensin-converting enzyme inhibitor
- Use of angiotensin II receptor blocker
- Use of statins
- Actual organ function evaluation
 - Respiratory rate
 - SpO₂; %
 - SpO₂/FiO₂
 - ROX index; SpO₂/FiO₂: RR
 - Dyspnea defined according to Borg dyspnea scale
 - Chest X-ray

- Non-invasive mean arterial pressure; mmHg
- Heart rate; BPM
- Body temperature; °C
- BUN, Creatinine, AST, ALT, Bilirubin, Hemoglobin, Platelets, PTT, WBC count
- SOFA score
- APACHE II, SAPS II; any of those used by the participating center

Post-randomization variables

One hour before each position change (supine and prone), the following variables will be collected for the duration of the protocol, which will be for 48 hours (APPENDIX v):

- Organ function evaluation:
 - Respiratory rate
 - SpO₂; %
 - SpO₂/FiO₂
 - ROX index; SpO₂/FiO₂: RR
 - Dyspnea defined according to the Borg dyspnea scale (APPENDIX v)
 - Non-invasive mean arterial pressure; mmHg
 - Heart rate; BPM
- Non-invasive support device parameters:
 - HFNC: flow; liters/min. FiO₂; %
 - CPAP: PEEP; cmH₂O. Flow; liters/min; Tidal volume; ml. FiO₂; %
 - NIV: PEEP; cmH₂O. Pressure support over PEEP; cmH₂O. Flow; liters/min. Tidal volume; ml. FiO₂; %
- Complications possibly related to prone position:
 - New hypotension (BPsys < 90mmHg or BPsys drop > 10mmHg, if BPsys < 90 before the maneuver)
 - New bradycardia (HR <50bpm or HR drop > 20%, if HR < 50 before the maneuver)
 - New hypoxemia (SpO₂ ≤ 90% or SpO₂ drop > 5%, if SpO₂ < 90% before the maneuver)
 - Ulcers
 - Displacements of any of the following: respiratory support device, peripheral or venous central line, oro or nasogastric tube, urinary catheter

Post-protocol variables

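### Section 8.2 names no baseline covariates for the confirmatory logistic model; fixing a short set before the first interim look would gain about 1 to 8 points of power, depending on how prognostic they are

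*Protocol*

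**What the plan says.** The primary endpoint (Protocol 7.1.1) is binary: "Rate of invasive mechanical ventilation during the first fourteen days of enrolment". For its analysis, section 8.2 says that "rates of invasive mechanical ventilation will be compared between the two intervention groups, and the odds ratio relative risks" with confidence intervals will come from logistic regression. No covariate is named. The word unadjusted does not appear either.

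Section 8.2 mentions covariate adjustment once, for time-dependent data in a proportional hazards model, where the covariates are to follow possible baseline imbalances. It also plans a comparison by COVID-19 status and a stratified analysis by respiratory support device. Only the primary outcome analysis is confirmatory, so all of these are exploratory.

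Section 7.2.4 lists the pre-randomization variables. They include age and, under "Actual organ function evaluation", respiratory rate, SpO2/FiO2, ROX index, Borg dyspnea and SOFA.

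Section 6.4 sizes the trial for the "prone position group of 24 % and the standard treatment group of 34 % (risk ratio of 0.70"), "assuming a twosided significance level of 0.05 and a power of 80"%. It states: "These calculations indicated that 322 patients would be required per group". With 10% dropout this becomes 714 in total ("n= 357 per group) were planned to be included in the study").

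Section 8.2 also refers to a statistical analysis plan to be completed before data collection ends, and schedules interim looks for efficacy and futility at N = 357 and N = 476.

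**The concern.** The confirmatory test already uses a regression model, and measures of the severity of respiratory failure are scheduled before randomization. Several of them match items in the intubation criteria of Appendix ii, such as respiratory rate and oxygen saturation. The population is also broad: failure from any cause, on Venturi mask, HFNC or NIV/CPAP. Baseline risk may therefore vary considerably between patients, and that is where adjustment pays.

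If the model contains treatment alone, the explainable variation stays in the error term. Power is lower than the same patients could give, and the result is more exposed to a chance severity imbalance between arms. Adjustment for prespecified covariates changes neither the number of patients, nor the endpoint, nor the type I error.

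Timing matters too. The primary statistic is used for stopping decisions at two looks before the end of data collection, which is the only deadline set for the analysis plan. Covariates chosen after a look would no longer be cleanly prespecified.

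**Working it through.** **Inputs from the protocol.** Rates 0.34 and 0.24, two-sided alpha 0.05, power 80%, 322 per group before dropout and 357 after (6.4); 1:1 allocation (7.2.1); final-look P boundary 0.044 (8.2).

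**Input not in the protocol.** R², the share of outcome variance explained by the baseline covariates. It is an assumption here, shown from 0.02 to 0.20.

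**Step 1: reproduce the plan's figure.** The mean rate is 0.29.

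n = [1.960 × √(2 × 0.29 × 0.71) + 0.8416 × √(0.34 × 0.66 + 0.24 × 0.76)]² / 0.10²
= [1.2577 + 0.5368]² / 0.01 = 322.0, which rounds up to 323.

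The arcsine formula gives exactly 322. Dropout: 322 / 0.9 = 357.8, against 357 stated. Unadjusted fixed-sample power is 80.0% at 322 per group and 83.9% at 357. The plan's calculation stands, and it assumes an unadjusted comparison.

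**Step 2: power with adjustment.** If covariates explain a share R² of the variance, the non-centrality is divided by √(1 − R²):

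power = Φ( (1.960 + z₀) / √(1 − R²) − 1.960 ), where z₀ is the normal quantile of the unadjusted power.

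Example at 322 per group, R² = 0.10: (1.960 + 0.8415) / √0.90 = 2.953; 2.953 − 1.960 = 0.993; Φ(0.993) = 84.0%.

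| Assumed R² | Power, 322 per group (gain) | Power, 357 per group (gain) |
|---|---|---|
| 0 | 80.0% | 83.9% |
| 0.02 | 80.8% (+0.8) | 84.6% (+0.7) |
| 0.05 | 82.0% (+2.0) | 85.7% (+1.8) |
| 0.10 | 84.0% (+4.0) | 87.5% (+3.6) |
| 0.20 | 87.9% (+7.9) | 91.0% (+7.1) |

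In patients, R² = 0.10 is worth 644 / 0.90 − 644 ≈ 72 more on 644.

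**Step 3: the final-look boundary.** If P ≤ 0.044 is treated as a single test at 322 per group, power is 78.4% unadjusted and 82.6% at R² = 0.10, a gain of 4.2 points. This ignores crossings at earlier looks.

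**Step 4: check by simulation.** One standard-normal baseline score was put into a logistic model with marginal rates held at 34% and 24%, 322 per group, 4,000 trials per setting. Wald tests of treatment with and without the score were compared.

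| AUC of the score | R² | Unadjusted | Adjusted |
|---|---|---|---|
| 0.61 | 0.032 | 79.2% | 80.5% |
| 0.66 | 0.064 | 79.6% | 82.4% |
| 0.70 | 0.103 | 81.2% | 84.9% |
| 0.74 | 0.144 | 80.5% | 87.1% |

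The simulated gains (+1.3, +2.8, +3.7, +6.6) agree with the formula within simulation error. The simulation tests the treatment coefficient of the adjusted logistic model, not a standardized risk ratio, so it supports the size of the gain only approximately for the latter.

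**The case against.** The strongest reply is that this rests on silence. The protocol never says the model is unadjusted, it refers to an analysis plan that is not shown, and covariate lists are commonly left to that plan. Part of this stands: an unadjusted model is the natural reading of section 8.2 and not its stated text. It does not settle the matter, because that plan need only exist before data collection ends, while the primary statistic is used at N = 357 and N = 476. The COVID-19 and device analyses do not settle it either, since they are exploratory and leave the confirmatory model unchanged.

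Second, an unadjusted intention-to-treat comparison is valid, controls type I error and matches the sample size calculation. That stands in full.

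Third, nothing shows that the covariates are strong. Entry requires respiratory rate above 25, SpO2 below 94% and FiO2 of at least 40%, and patients who already meet intubation criteria are excluded. This narrows the range of the very variables proposed and may weaken their prediction. That also stands, and it is why the gain is given as a range that starts below 1 point.

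Fourth, completeness is not assured. Section 7.2.4 lists the variables, but the Appendix v timetable has no baseline row for ROX, Borg or SOFA and marks respiratory variables only during the intervention. The number of missing baseline values is therefore unknown.

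Fifth, an adjusted odds ratio is conditional and differs from the marginal one, so adjustment touches the estimand unless it is stated. The fix has to cover this.

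**Conclusion.** The point holds as a missed efficiency gain. Section 8.2 names no baseline covariates for the one confirmatory comparison, although suitable variables are scheduled before randomization. The gain over 80.0% power at 322 per group is about 1 to 2 points if they explain 2% to 5% of outcome variance, 4 points at 10% and 8 points at 20%, and slightly less at 357 per group. All of these rest on an assumed R².

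A reader might infer more, and the documents do not support it:

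- That the baseline measures are strong predictors and the loss is a definite 3 to 9 points. That range needs an R² of about 0.08 to 0.22, for which the protocol gives no evidence.
- That the trial has no margin. It randomizes 357 per group and analyzes all as randomized; if 14-day outcomes are nearly complete, unadjusted fixed-sample power is 83.9%.
- That adjustment is free. It is cheap, but it needs a rule for missing values and a stated estimand.
- That the planned test is wrong. It is not.

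**What to change.** Amend section 8.2 before the first interim look so that:

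1. The primary logistic model contains treatment plus a short fixed covariate set already listed in section 7.2.4, for example baseline ROX index, age and SOFA. ROX already combines SpO2/FiO2 and respiratory rate, so those need not be added beside it. APACHE II and SAPS II are unsuitable, since the choice between them varies by center.
2. The reported effects are the marginal risk ratio and risk difference, obtained by standardizing the model's predictions, with a standard error that matches that estimator. This keeps the result on the risk-ratio scale of section 6.4.
3. The statistic compared with the boundaries is named, and the same adjusted statistic is used at every look.
4. The unadjusted comparison is kept as a sensitivity analysis.
5. Missing baseline values are handled by a simple prespecified imputation, so that no randomized patient is dropped.

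The cost is one paragraph and slightly more analysis code. No new variables are needed, though the Appendix v timetable should show the chosen ones at baseline. Sample size and endpoint do not change.

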6. STUDY POPULATION

6.1 Population (base)

We intend to recruit acute hypoxemic respiratory failure patients with a respiratory rate of more than 25 breaths per minute, $SpO_2 < 94\%$ and FiO_2 of at least 40% or more by either Venturi facemask, HFNC, or NIV/CPAP and, absence of decompensated respiratory acidosis during two years. Currently, we expect about 35 centers to participate in the trial.

Demographic data and clinical characteristics on screened patients, regardless of enrolment criteria match, will be recorded (registry). We will randomize 714 patients admitted to the participating centers' intensive care units and expect each participating center to randomize at least 25 patients who meet all inclusion criteria.

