7.2.1 Randomization

Randomization procedure

Randomization will be performed using a dedicated website and will be balanced per center. *Randomization arms*

Central randomization with the use of a permutated-block randomization list (block length 6) will be used. Participants will be allocated to the prone position or standard care on a 1:1 ratio. At each site, at least two investigators will be involved: one who will be aware of the allocated intervention and collect the data; the other will remain blinded to the interventions and evaluate the outcomes.

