7.2.3 Standard management

The standard management of patients with acute hypoxemic respiratory failure will be done according to the usual practices of each participating center.

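### Randomization is balanced per center, but the primary analysis in 8.2 names no center term: a slightly conservative test that one sentence would correct

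*Protocol*

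**What the plan says.** On allocation, Protocol 7.2.1 states: "Randomization will be performed using a dedicated website and will be balanced per center". It uses permuted blocks of 6 and a 1:1 ratio. Center is the only balancing factor named.

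On the primary analysis, Protocol 8.2 states that "rates of invasive mechanical ventilation will be compared between the two intervention groups", with the effect measure and its 95% interval taken from logistic regression. No model terms are listed. The same section mentions baseline adjustment only for time-dependent data, and stratified analysis only by respiratory support device.

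On how much centers may differ, Protocol 6.1 says: "Currently, we expect about 35 centers to participate in the trial". Protocol 7.2.3 says that standard management "will be done according to the usual practices of each participating center". No between-center variation in intubation is given anywhere.

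Protocol 8.2 also leaves detail to a separate statistical analysis plan, due before data collection ends. That plan is not at hand.

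**The concern.** When arms are balanced within center, differences between centers largely cancel out of the treatment comparison. The true sampling variance of the difference in rates then contains only within-center variation. A pooled two-group comparison still uses the total variance, within plus between. If centers differ, its standard error is too large, so its P-value is too high on average and its interval too wide.

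This touches the only analysis that the protocol calls confirmatory, and the interim looks that use it. What is at stake is some efficiency, and agreement between the stated P-value and the way patients were allocated. It does not put the validity of a positive result at risk.

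**Working it through.** **1. The plan's own figure.** Protocol 6.4 takes a "rate of mechanical ventilation between the prone position group of 24 % and the standard treatment group of 34 % (risk ratio of 0.70"), two-sided 0.05 and 80% power. With the pooled formula for two proportions and mean rate (0.34 + 0.24)/2 = 0.29:

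n = [1.96·√(2·0.29·0.71) + 0.8416·√(0.34·0.66 + 0.24·0.76)]² / 0.10²
= [1.96·0.6417 + 0.8416·0.6378]² / 0.01 = (1.7946)² / 0.01 ≈ 322.0

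This rounds up to 323, and the protocol says: "These calculations indicated that 322 patients would be required per group". With 10% dropout, 322/0.9 = 357.8, against 357 stated. The figure reproduces as a calculation without a center term.

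**2. Assumption for centers.** Each center has a normal random intercept on the logit scale with standard deviation SD. The marginal rates are held at 34% and 24%. SD is not in the documents, so a range is shown. As a guide, the 10th to 90th percentiles of center control rates are 21%-48% at SD 0.5, 15%-55% at SD 0.75 and 11%-62% at SD 1.0.

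**3. Size of the standard error.** Total variance per patient at the mean rate is 0.29·0.71 = 0.2059. The within-center part is the average of p(1−p) over the center distribution, found by numerical integration.

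- SD 0.5: within-center 0.1961; ratio of standard errors √(0.2059/0.1961) = 1.025. The nominal cut-off of 1.96 acts like 1.96·1.025 = 2.01, so type I error is about 4.5%.
- SD 1.0: within-center 0.1739; ratio √(0.2059/0.1739) = 1.088. The cut-off acts like 2.13, so type I error is about 3.3%.

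The interval for the risk difference is therefore about 2.5% to 9% too wide over this range.

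**4. Power at 357 per group, SD 1.0 as the example.** The standard error of the difference under the planned rates is about 0.0310.

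- Without center: critical difference 1.96·√(2·0.2059/357) = 0.0666; power Φ[(0.10 − 0.0666)/0.0310] ≈ 86%.
- With center: critical difference 1.96·√(2·0.1739/357) = 0.0612; power Φ[(0.10 − 0.0612)/0.0310] ≈ 89%.

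**5. Simulation.** 714 patients, 35 centers of unequal size, blocks of 6 within center, two-sided 0.05. The pooled two-proportion test is compared with the Cochran-Mantel-Haenszel (CMH) test

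z = Σ(a_k − t_k·m_k/n_k) / √Σ[t_k·c_k·m_k·(n_k − m_k) / (n_k²·(n_k − 1))],

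where in center k, a is prone-arm events, t and c are the arm sizes, m is total events and n is total patients. Ranges show the spread between separate simulations.

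| SD (logit) | Type I error, no center | Power gain from stratifying, n = 714 | Gain, n = 644 |
|---|---|---|---|
| 0 | about 5% | −0.3 (83.9% to 83.6%) | – |
| 0.5 | 4.2%-4.8% | 0.9-1.1 points | 1.1 |
| 0.75 | 3.9% | 1.8-1.9 | 2.3 |
| 1.0 | 3.4%-3.6% | 3.2-3.4 | 3.7 |

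At SD 0.3 or below the simulated gain is not material. The direction and size are similar with 28 centers (714/25 ≈ 28, from the expectation of at least 25 patients per center in 6.1). At the first interim look (357 patients, P ≤ 0.006) the gain for SD 0.5 to 1.0 is about 1 to 6 points.

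**6. Planned power.** At 322 per group the approximation gives a power without center of 80.0% if centers are alike, 80.8% at SD 0.60 and 82.6% at SD 1.19. It does not fall below the planned 80%.

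**The case against.** The strongest reply is that 8.2 lists no model terms at all, so center is not ruled out, and the separate analysis plan may include it. This stands. A reader might infer that the sponsor has decided to ignore center. The protocol does not say that; it says only what is compared and by which method. Two things keep the point alive. First, 8.2 assigns adjustment and stratification to other analyses and gives the primary comparison neither. Second, the analysis plan is due only before data collection ends, while interim looks are set at 357 and 476 patients. At those looks the protocol text could be the only specification.

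The second reply is that the size is assumed. This also stands. A reader might take 1 to 4 points as a known loss, but the documents give no between-center variation. The loss is under half a point at SD 0.26 and 4 to 5 points at SD 1.19. The common intubation criteria in Appendix ii and the shared entry thresholds in sections 5 and 6.1 may keep centers closer together than local standard care alone would suggest.

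The third reply is that nothing planned is broken. A reader might infer an underpowered trial or an inflated false-positive rate. Neither follows: type I error is below nominal, and power is forgone only against a more efficient analysis.

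**Conclusion.** The point holds as a low-cost improvement. The design balances on center, and the stated primary analysis names no center term. If the analysis is run that way and centers differ with a logit SD of 0.5 to 1.0, the test runs at about 4.8% to 3.4% and forgoes about 1 to 4 points of power relative to a center-stratified analysis. With SD 0.3 or below there is nothing material to gain.

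The direction rests on the balanced allocation alone. The size rests on the assumed SD, a normal distribution of center effects and roughly 20 to 25 patients per center. The too-wide interval applies to the risk difference, the relative risk and the marginal odds ratio. The statement that 80% power is kept refers to the fixed-sample calculation at two-sided 0.05. What the stricter final boundary of 0.044 does to power is a separate matter.

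**What to change.** In 8.2, state that the primary comparison is stratified by center, using the Cochran-Mantel-Haenszel test with the Mantel-Haenszel risk ratio and risk difference and their 95% confidence intervals. State that the same statistic is used at each interim look and at the final look. Carry the same wording into the analysis plan before the first look.

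Do not offer a random-intercept logistic model as an interchangeable option. Its odds ratio is conditional on center, lies further from 1 than the marginal one, and need not have a smaller log-scale standard error. If such a model is kept, say that its odds ratio is conditional on center.

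The cost is one sentence. Center is known for every patient, so no data are added. Centers with patients in only one arm contribute nothing to the stratified estimate, which is a small loss at about 20 patients per center (714/35) but matters more at the first look, with about 10 (357/35). If centers turn out not to differ, up to about half a point of power is given up.
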